Progression-Free Survival (PFS) is defined as the duration of time from start of treatment to time of recurrence, progression, or death, whichever occurs first.

Survival

Survival is defined as the duration of time from start of treatment to time of death or the date of last contact whichever occurs first.

Permitted Deviations from RECIST

The study's efficacy objectives will be evaluated according to the standard, unmodified RECIST v1.1 criteria described in section 12.3, and that, within the context of this protocol, the only purpose of the modifications to the criteria is to allow certain patients to continue the study treatment despite meeting RECIST criteria for progression of disease.

The response to immunotherapy may differ from the typical responses observed with cytotoxic chemotherapy including the following ([name] et al 2009, Nishino et al 2013):

- Response to immunotherapy may be delayed
- Response to immunotherapy may occur after POD by conventional criteria
- The appearance of new lesions may not represent POD with immunotherapy
- SD while on immunotherapy may be durable and represent clinical benefit.

Date:

As long as they are receiving treatment on protocol, patients will be permitted to continue study treatment after RECIST v 1.1 criteria for POD are met if they meet all of the following criteria:

- Absence of symptoms and signs indicating unequivocal progression of disease
- No decline in ECOG performance status
- Absence of tumor growth at critical anatomical sites (e.g., leptomeningeal disease) that cannot be managed by protocol-allowed medical interventions
- Patients for whom approved therapies exist must provide verbal consent to acknowledge deferring these treatment options in favor of continuing study treatment at the time of initial apparent progression

Patients with radiographic disease progression at the at subsequent tumor assessment may be considered for continued study treatment at the discretion of the investigator if they continue to meet the criteria above and have evidence of clinical benefit.

Modification of RECIST as described may discourage the early discontinuation of durvalumab and tremelimumab and provide a more complete evaluation of its anti-tumor activity than would be seen with conventional response criteria. Nonetheless, the efficacy analysis will be conducted by programmatically deriving each efficacy endpoint based on RECIST v 1.1 criteria.

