If the test for ORR is significant, then the PFS rate at 24 weeks (+/- 1 week) will also be tested against the historical control estimate. For PFS rate at 24 weeks (+/- 1 week), we consider a 15% rate as low, and a rate of 35% or higher as indicative of promising activity. This stems from Gynecologic Oncology Group studies of the same patient population we are evaluating in this study which have deemed PFS at 6 months of 15% or less as indicative of lack of activity and PFS at 6 months of 35% or more as indicative of having activity.

This test of PFS rate will be performed only if the ORR analysis is significant, and thus PFS assessment is supplementary to ORR assessment. At the end of the study, if 10 or more out of 40 patients are considered progression free at 24 weeks (+/- 1 week), then that arm will be considered worthy of further study. This study will have 94% power and 7% Type I error to show activity in terms of 6 months PFS rate. The overall Type I error of the study is bounded by the 10% error rate of the first hypothesis of ORR. The hierarchy in the two hypotheses for ORR and PFS ensures the overall error rate to be smaller than 10% (Bretz 2009)

If both arms have ≥ 7 responders the winning arm is the one with higher ORR and if both arms have exactly 7 responders the winning arm will be decided based on the review of all efficacy data (ORR and PFS) and the total safety profile (number and type of grade 3 AE) of each arm.

A treatment arm will be considered promising if the ORR decision rule is met, but the 6 month PFS decision rule is not met. After first stage accrual is complete, we will halt the study for 16 weeks after last patient has been accrued to first stage in order to assess the decision rules to move to stage 2. Based on historical accrual rates in similar populations, we anticipate successful enrollment of 4 patients per month yielding a total accrual time of 20 months. Accrual will continue until 40 patients on each arm (evaluable patients are defined in section 12.1), unless the interim analysis after 27 patients does not support continuation.

Definitions of Statistics to be Reported

- Clinical Benefit Rate (CBR), defined as the percentage of patients with complete response (CR) + partial response (PR) + stable disease (SD) by 24 weeks from the start of treatment will be reported and the 90% confidence interval will be estimated using exact binomial proportions. This will be done following RECIST criteria.

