- Progression free survival (PFS), defined as the duration of time from start of treatment to time of recurrence, progression, or death due to any cause, whichever occurs first. Patients will be censored at last follow up date. The Kaplan Meier estimate of median PFS will be reported as well as the PFS rate at 24 weeks (+/- 1 week).
- Duration of response (DOR), defined as the time from which measurement criteria are met for CR or PR (whichever status is recorded first using RECIST) until the first date of documented

Date:

disease progression, will be estimated using the Kaplan Meier method. Patients without documented progression will be censored at last follow up.

- The rate of response using immune response criteria (refer to irRECIST description in section 12.3, which defines responders and non responders) and the 90% confidence interval will be estimated using exact binomial proportions.
- Adverse events by the current version of Common Terminology Criteria for Adverse Events version 4 (CTCAE v4.03) will be tabulated in order to assess the safety profile and tolerability therapy in treated patients.

Safety Analysis

The frequency and severity of observed adverse effects will be evaluated. The rates of irAE, SAE, therapy completion rate, and protocol completion will also be reported.

Safety will be measured by the frequency of grade 3 or 4 treatment-related clinically significant toxicities (NCI Common Terminology Criteria for Adverse Events version 3.0), aside from Grade 3 or 4 hematologic or laboratory abnormalities, unless they are deemed unexpected or clinically significant.

Frequencies of toxicities will be tabulated. The grade 3 or 4 treatment-related non-hematologic/non-laboratory toxicity will be estimated at the end of the trial along with the 95% confidence interval. With 40 patients per arm, these rates can be estimated within $\pm 16\%$.

Methods of Efficacy Analysis

Efficacy Variables

The intent of this protocol is to assess checkpoint inhibitors for activity in patients with carcinomas advanced, recurrent endometrial carcinomas and carcinosarcomas.

The principal parameters employed to evaluate the efficacy of the two arms are:

- The rate of ORR and duration of overall objective response (ORR = CR + PR).
- Progression-free survival rate at 24 weeks for all patients evaluable for this endpoint.
- Clinical Benefit Rate (CBR) will be defined as ORR + Stable Disease (SD) rate by 24 weeks.

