Patients who have measurable disease present at baseline, have received at least one cycle of therapy, and have had their disease reevaluated will be considered evaluable for response and PFS. The primary efficacy analysis will include only patients who are evaluable for response. Patients without post baseline assessment of response will be included in a sensitivity analysis as non responders for ORR, and events for PFS. A 90% confidence interval for PFS will also be provided.

All patients will be followed up for a minimum of 6 months. We do not expect any patient to have a follow up of less than 6 months. If a patient meets all the criteria for being evaluable but has not been followed for 6 months and has not progressed, this patient will be censored at the time of last follow up. This patient will be included in the analysis. For the determination of the decision rule for PFS (ie ≥ 10 patients event free), this patient will be considered a failure.

Date:

For safety, all patients who received at least one cycle of therapy will be included.

As per the standard of reference set by the Gynecologic Oncology Group for recurrent endometrial cancers, if a new agent has a true response rate of 10% or less, it would be considered of little clinical significance. Conversely, if the true response rate is at least 25%, further investigation is clearly indicated. These are the reference ORR numbers used to assess novel agents in the GOG-129 and 229 queue, through which nearly 20 treatments have been evaluated. As a means of comparison, and to further justify this ORR goal, the clinical data for several relevant cytotoxic and biologic agents are tabulated here.

Rx	ORR (%) [PR + CR]	PFS at 24 weeks (%)	# of Patients (n)	Reference
Etoposide	0	8.0	25	Rose et al, Gynecol Oncol 1996
Paclitaxel	25	20.8	48	Ball et al, Gynecol Oncol, 1996
Doxorubicin	9.3	23.3	43	Thigpen et al, Cancer Treat Rep. 1979,
Ixabepilone	12	20.4	49	Dizon et al, JCO, 2009
Bevacizumab	17	41.5	53	Aghajanian et al, JCO, 2011

Given the inherent difficulty in detecting meaningful overall survival (OS) data in patients who will likely frequently receive multiple, and divergent downstream agents after end of study, including possible enrollment in additional clinical trials, PFS at 24 weeks (6 months) is considered an appropriate endpoint for meaningful clinical efficacy. (Sill 2008) This approach has been adopted for recurrent and advanced endometrial cancer.

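### The primary ORR and 24-week PFS analyses leave out treated patients who are never re-evaluated, and the analysis that counts them as failures has no stated role in the decision rules

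*Combined protocol and SAP*

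**What the plan says.** Section 14.0, Methods of Efficacy Analysis, says that patients with measurable disease at baseline who "have received at least one cycle of therapy, and have had their disease reevaluated will be considered evaluable for response and PFS". It then limits the primary set: "The primary efficacy analysis will include only patients who are evaluable for response". The remaining treated patients are handled separately: "Patients without post baseline assessment of response will be included in a sensitivity analysis as non responders for ORR, and events for PFS".

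Both PFS definitions count death as an event. Section 12.4 measures PFS as the "duration of time from start of treatment to time of recurrence, progression, or death, whichever occurs first"; Section 14.0 runs it to "time of recurrence, progression, or death due to any cause, whichever occurs first".

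The decision rules in Section 14.0, per arm, are at least 3 responders of 27 at the interim, at least 7 of 40 at the end, and then at least 10 of 40 progression-free at 24 weeks. If both arms reach 7 responders, "the winning arm is the one with higher ORR"; a 7-7 result goes to a review of all the data.

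On the denominator, Section 14.0 counts the interim 27 as evaluable patients and, for accrual to 40 per arm, points to the evaluable definition. Against that, Section 1.1 gives 80 patients, Section 9.1 says withdrawn patients are not replaced, and Section 14.0 states that "we anticipate successful enrollment of 4 patients per month yielding a total accrual time of 20 months", which is 4 × 20 = 80.

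**The concern.** A patient who is treated and dies before the first scan is a PFS event by definition, yet is absent from the primary PFS set. For ORR the same patient is neither a responder nor a non-responder. No section says that the failure-counting analysis governs the interim rule, the final rules or the choice of winning arm.

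Three things are at stake: an upward tilt in the headline ORR and PFS, a winning-arm comparison that may use different denominators in the two arms, and, under one reading of the accrual target, the 10% bound on type I error that Section 14.0 claims.

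The group is narrow. Section 12.1 keeps patients with objective progression before the end of cycle 1 (Section 14.0 repeats the definition without that note). Section 4.3 allows patients who stop treatment without progression to go on being scanned.

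**Working it through.** **Inputs.** From Section 14.0: ORR 10% v 25%, rules 3/27 and 7/40; 24-week PFS 15% v 35%, rule 10/40. The fraction q of treated patients never assessed is not in the documents; I assume 2.5%, 5% and 10%, all of them failures. That is an upper bound for PFS, because some may be lost without having progressed.

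**Step 1: the plan's own figures.** ORR pass probability = Σ over x ≥ 3 of P(X₁ = x; 27, p) × P(X₂ ≥ 7 − x; 13, p).
- ORR: 0.0977 at p = 0.10 and 0.9001 at p = 0.25 (stated: 10% and 90%).
- PFS: P(X ≥ 10; 40, 0.15) = 0.0672 and P(X ≥ 10; 40, 0.35) = 0.9356 (stated: 7% and 94%).

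All four reproduce.

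**Step 2: reported rates with 40 treated per arm.** An unassessed patient adds nothing to the numerator and leaves the denominator.

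| Unassessed | 7 responders | 10 progression-free |
|---|---|---|
| 0 | 7/40 = 17.5% | 10/40 = 25.0% |
| 2 | 7/38 = 18.4% | up to 10/38 = 26.3% |
| 4 | 7/36 = 19.4% | up to 10/36 = 27.8% |

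**Step 3, reading (a): 40 treated per arm, no replacement.** The counts 7 and 10 are the same whether or not the unassessed are in the denominator, so the final decisions do not change. The 27th evaluable patient may arrive when 27 to 40 have been treated; ORR type I error is then 0.0977 to 0.0995, and PFS stays at 0.0672.

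The winning-arm rule does change, because it compares rates. Take a true all-treated ORR of 25% in both arms, responders following the two-stage distribution of Step 1, and both arms passing (0.9001² = 0.810). Compare X_A/(40 − u) with X_B/40, where u is the number unassessed in arm A and arm B has none.

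| u v 0 | Arm with losses wins | Other arm wins | Tied or 7-7 | Arm with fewer responders wins |
|---|---|---|---|---|
| 0 | 43.9% | 43.9% | 12.2% | – |
| 1 | 55.2% | 43.9% | 0.9% | 0 |
| 3 | 55.9% | 43.2% | 0.9% | 0.7% |
| 4 | 61.0% | 35.7% | 3.3% | 5.7% |

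At 1 v 0 the gain of 55.2 − 43.9 = 11.3 points is entirely exact count ties being broken. Arm A with a responders beats a + 1 in arm B only if a/(40 − u) > (a + 1)/40, that is a > (40 − u)/u:
- u = 1: a > 39, impossible with 39 assessed.
- u = 2: a > 19, with negligible probability.
- u = 3: a > 12.3.
- u = 4: a > 9; for example 10/36 (27.8%) beats 11/40 (27.5%).

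**Step 4, reading (b): accrual to 40 evaluable per arm.** If the 10% benchmark is an all-treated rate, the null among evaluable patients is 0.10/(1 − q). Total treated is 80/(1 − q).

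| q | Null among evaluable | ORR type I error | Total treated |
|---|---|---|---|
| 0 | 10.0% | 9.8% | 80 |
| 2.5% | 10.3% | 10.8% | 82.1 |
| 5% | 10.5% | 12.0% | 84.2 |
| 10% | 11.1% | 14.7% | 88.9 |

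If the benchmark is an evaluable-set rate, ORR type I error stays at 9.8%. Under reading (b) both arms have 40 in the denominator, so Step 3 does not apply.

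**The case against.** The plan already contains the requested analysis for both endpoints, so both results would be available; what remains is which one is primary. Section 6.2 requires a life expectancy of at least 12 weeks and ECOG 0 or 1, and the first scan is due at 8 weeks ± 7 days, which argues for few unassessed patients. Section 14.0 says that the trial is not powered to compare the arms, and in the Step 3 model both arms are equally good, so neither choice is wrong. The denominator is also less open than it looks: Section 14.0 leans towards evaluable patients, the no-replacement sentence in Section 9.1 concerns withdrawals, and 4 per month is a forecast, not a cap.

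Most of this stands and limits the size of the point. It does not remove it: the primary set still omits deaths that the endpoint counts, and the sensitivity analysis still has no decision role. The rule in Section 14.0 that counts short follow-up as failure for PFS covers only patients who already meet the evaluable criteria.

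A reader might infer that the losing arm is routinely selected. The documents do not support that: reversals are absent or negligible at 1 or 2 unassessed against 0, and remain uncommon at 4 against 0.

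**Conclusion.** The point holds as a matter of analysis set and should be fixed. Reported ORR exceeds the all-treated rate whenever a treated patient is unassessed (17.5% becomes 18.4% or 19.4% with 2 or 4 of 40). PFS does too, to the extent that those patients died or progressed. This needs no assumption about benchmarks.

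Beyond that there are two alternatives, which cannot both occur:
- **40 treated per arm:** the final count rules are unaffected, and the winning-arm rule tilts towards the arm with more early losses, mainly by breaking ties.
- **40 evaluable per arm**, which the wording of Section 14.0 favours: ORR type I error passes the 10% bound only if 10% is an all-treated rate. Section 14.0 says that "if a new agent has a true response rate of 10% or less, it would be considered of little clinical significance" but does not say among whom. The lower end, 10.8%, is more plausible given the entry criteria.

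A reader might infer that the stated error rates are wrong. They are not shown to be: all four reproduce, and inflation is conditional on two unstated facts (the benchmark denominator and q). PFS error is secondary, since PFS is tested only after ORR succeeds and an arm is called promising on ORR alone.

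**What to change.** In Section 14.0, make the existing failure-counting analysis of all treated patients primary for ORR and 24-week PFS. No post-baseline assessment counts as a non-responder and a PFS failure, and a death is an event at its date. Define the 27 and 40 per arm as treated patients, and state that this analysis governs 3/27, 7/40, 10/40 and the winning-arm comparison. Keep the evaluable-only result as supportive.

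Also:
- State whether the 10%/25% and 15%/35% benchmarks refer to treated or evaluable patients.
- Carry the Section 12.1 note on progression before the end of cycle 1 into Section 14.0.
- Reconcile Section 9.1 with Section 14.0 on replacement.

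The change needs new wording and no new data. Reported rates would be slightly lower. If 25% and 35% are all-treated rates, power is unchanged. If they are evaluable-set rates, each is multiplied by 1 − q, and power with 40 treated per arm falls:

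| q | ORR power | PFS power |
|---|---|---|
| 0 | 90.0% | 93.6% |
| 2.5% | 88.4% | 92.0% |
| 5% | 86.6% | 90.2% |
| 10% | 82.2% | 85.5% |

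In that case, restate the power rather than enrol more patients.

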4.1 OVERVIEW OF STUDY DESIGN/INTERVENTION

4.2 Design

This is an MSKCC investigator-initiated, single-center, randomized, open-label, phase 2 study to evaluate the activity of durvalumab alone (Arm 1) or durvalumab in combination with tremelimumab (Arm 2) in patients with recurrent or persistent endometrial carcinoma or endometrial carcinosarcoma. The safety and tolerability of these agents in this patient population will also be evaluated.

Patients will be randomized to Arm 1: durvalumab alone or Arm 2: durvalumab with tremelimumab. Randomization will be accomplished by the method of random permuted block, and patients will be stratified by histology (stratum 1: endometrial carcinosarcoma patients OR MSI-high endometrial carcinoma patients and stratum 2: other histologies). We will limit enrollment of stratum 1 to 10 patients per arm.

MSI-high patients will be identified based on immunohistochemistry or MSI testing of tumor by department of pathology or via known mutations found in mismatch repair genes via the Integrated Mutation Profilng of Actionable Cancer Targets (IMPACT) assay through MSKCC IRB# 12-245.

Each cycle will be 28 days in duration. Patients will receive study treatment until disease progression, intolerable toxicity, elective withdrawal from the study, study completion, or study termination.

Radiologic tumor assessment will be repeated every 8 weeks +/- 7 days for the first 48 weeks and then every 12 weeks +/- 7 days until PD. For patients who remain progression free 2 years post completion of protocol directed treatment, every 6 months +/- 1 month. Safety will be evaluated through the monitoring of all serious and non-serious AEs and irAE's, graded according to the current version of National Cancer Institute's Common Terminology Criteria for Adverse Events (CTCAE v. 4.03).

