Vials should be used for specific subjects and should not be shared between subjects.

Patient weight at baseline should be used for dosing calculations in patients ≤ 30 kg unless there is a $\geq 10\%$ change in weight. Dosing day weight can be used for dosing calculations instead of baseline weight per institutional standard.

Dose administration

Durvalumab will be administered at room temperature (approximately 25°C) by controlled infusion via an infusion pump into a peripheral or central vein.

Following preparation of Durvalumab, the entire contents of the IV bag should be administered as an IV infusion over approximately 60 minutes (± 5 minutes), using a 0.2- μm in-line filter. Less than 55 minutes is considered a deviation.

The IV line will be flushed with a volume of normal saline equal to the priming volume of the infusion set used after the contents of the IV bag are fully administered, or complete the infusion according to institutional policy to ensure the full dose is administered and document if the line was not flushed.

The Durvalumab solution should not be infused through an IV line in which other solutions or medications are being administered.

Monitoring of dose administration

Subjects will be monitored during and after the infusion with assessment of vital signs at the times specified in the Schedule of Assessments (Section 10.0).

In the event of a Grade ≤ 2 infusion-related reaction, the infusion rate of study drug may be decreased by 50%, or interrupted until resolution of the event (up to 4 hours) and re-initiated at 50% of the initial rate until completion of the infusion. For subjects with a Grade ≤ 2 infusion-related reaction, subsequent infusions may be administered at 50% of the initial rate. Acetaminophen and/or an antihistamine (e.g., diphenhydramine) or equivalent

Date:

medications per institutional standard may be administered at the discretion of the investigator. If the infusion-related reaction is Grade ≥ 3 or higher in severity, study drug will be discontinued.

As with any antibody, allergic reactions to dose administration are possible. Appropriate drugs and medical equipment to treat acute anaphylactic reactions must be immediately available, and study personnel must be trained to recognize and treat anaphylaxis. The study site must have immediate access to emergency resuscitation teams and equipment in addition to the ability to admit subjects to an intensive care unit if necessary.

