12.1 Definitions

Evaluable for toxicity. All patients will be evaluable for toxicity from the time of their first treatment on study.

Evaluable for objective response. Only those patients who have measurable disease present at baseline, have received at least one cycle of therapy, and have had their disease reevaluated will be considered evaluable for response. These patients will have their response classified according to the definitions stated below. (Note: Patients who exhibit objective disease progression prior to the end of cycle 1 will also be considered evaluable.)

Evaluable Non-Target Disease Response. Patients who have lesions present at baseline that are evaluable but do not meet the definitions of measurable disease, have received at least one cycle of therapy, and have had their disease reevaluated will be considered evaluable for non-target disease. The response assessment is based on the presence, absence, or unequivocal progression of the lesions.

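### Section 14 limits the safety set to patients who received at least one cycle, which conflicts with Section 12.1 and can drop patients because of the toxicity being measured

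*Combined protocol and SAP*

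**What the plan says.** The protocol describes the safety population in three places.

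- Section 14.0, Methods of Efficacy Analysis: "For safety, all patients who received at least one cycle of therapy will be included".
- Section 12.1, Definitions: "All patients will be evaluable for toxicity from the time of their first treatment on study".
- Section 14.0, Definitions of Statistics to be Reported: adverse events "will be tabulated in order to assess the safety profile and tolerability therapy in treated patients".

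The Safety Analysis subsection of Section 14.0 sets no cycle requirement. It says: "The grade 3 or 4 treatment-related non-hematologic/non-laboratory toxicity will be estimated at the end of the trial along with the 95% confidence interval". It gives a precision of ±16% for 40 patients per arm.

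On the length of a cycle, Section 4.2 says: "Each cycle will be 28 days in duration". The response-evaluable definition in Section 12.1 also requires at least one cycle of therapy, and then adds a note: "Patients who exhibit objective disease progression prior to the end of cycle 1 will also be considered evaluable". The safety sentence carries no such note.

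**The concern.** A safety set should not depend on how a patient tolerated treatment. If entry requires a cycle to have been received, an event severe enough to stop treatment early can also remove the patient from the analysis of that event. Section 5.2 provides one such route: "If the infusion-related reaction is Grade ≥ 3 or higher in severity, study drug will be discontinued". A Grade 3 or higher reaction during the first infusion ends treatment on the first day.

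The irAE rate, the SAE rate and the safety of each arm are secondary endpoints in Section 2.1. Safety also enters the choice of arm when both arms have exactly 7 responders, through "the total safety profile (number and type of grade 3 AE) of each arm". Any exclusion caused by toxicity would make the regimen look safer than it is.

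**Working it through.** **1. The plan's own precision figure.** Inputs from Section 14.0, Safety Analysis: n = 40 per arm, 95% confidence. At the worst case p = 0.5:

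- Wald half-width = 1.96 × √(0.25/40) = 15.5%.
- Exact (Clopper-Pearson) for 20/40: 33.8% to 66.2%, half-width 16.2%.

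Both agree with the stated ±16%, so the plan's own calculation puts all 40 patients per arm in the safety denominator. With 4 excluded (n = 36) the Wald half-width is 16.3%. Precision hardly moves; the issue is bias.

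**2. What one cycle can mean.**

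| Reading | Support in the protocol | Who is left out |
|---|---|---|
| Completed 28-day cycle | Cycle length in Section 4.2. The Section 12.1 note on progression before the end of cycle 1 would be largely unnecessary if a Day 1 dose already counted as a cycle | Anyone who stops in cycle 1, including for toxicity |
| Day 1 dosing given | Study drug is scheduled only on Day 1 of each cycle (Section 10.0). The combination paragraph of Section 5.2 uses doses and cycles interchangeably | Only patients whose first dosing day is not completed |

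The second reading still leaves a gap. In Arm 2 tremelimumab is infused first and durvalumab starts about 1 hour after it ends (Section 4.3). An Arm 2 patient who stops after a Grade 3 or higher reaction to the first tremelimumab infusion has not received that cycle's durvalumab. An Arm 1 patient whose first infusion is abandoned is in the same uncertain position.

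**3. Effect on a rate.** Let x of n treated patients have the event, and suppose k of those x are excluded. The reported rate is (x − k)/(n − k) instead of x/n, an understatement of k(n − x)/[n(n − k)]. For x = 12, n = 40, k = 2 this is 2 × 28/(40 × 38) = 3.7 percentage points.

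The documents give neither k nor x for this trial. Both are assumptions here: k from 0 to 4, and two base rates. The 10% base is close to the 9.4% of treatment-related Grade 3 or higher events that Section 3.0 reports for durvalumab monotherapy in Study 1108. The 30% base is purely illustrative.

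| Excluded (k) | True 12/40 (exact 95% CI) | True 4/40 (exact 95% CI) |
|---|---|---|
| 0 | 12/40 = 30.0% (16.6–46.5) | 4/40 = 10.0% (2.8–23.7) |
| 1 | 11/39 = 28.2% (15.0–44.9) | 3/39 = 7.7% (1.6–20.9) |
| 2 | 10/38 = 26.3% (13.4–43.1) | 2/38 = 5.3% (0.6–17.7) |
| 4 | 8/36 = 22.2% (10.1–39.2) | 0/36 = 0% (0–9.7) |

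**4. Reach into the arm choice.** Safety counts in the winning-arm rule only if both arms finish with exactly 7 responders. Under the two-stage rule (at least 3 of 27, then 40 in total), the probability that one arm ends with exactly 7 is the sum over x = 3 to 7 of P(x of 27) × P(7 − x of 13). Squaring it, for independent arms with equal true ORR, gives:

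- ORR 10%: 0.056² = 0.3%.
- ORR 17.5%: 0.160² = 2.5%, near the maximum.
- ORR 25%: 0.083² = 0.7%.

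**The case against.** The strongest reply is that this is loose wording, not a plan to discard early toxicity. Two of the three statements already cover all treated patients, the restrictive one sits under an efficacy heading, and with Day 1-only dosing a patient who was dosed may well be said to have received a cycle. On that reading an immune event on Day 10 or a death on Day 20 stays in the set. Adverse events are recorded from consent to 90 days after the last dose (Section 17), so nothing is lost from the database. The illustrated shifts also lie inside the plan's own ±16%.

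Much of this stands, and it limits the point. It does not remove it: the sentence that names who is included for safety is the restrictive one, nothing says which statement prevails, and patients with an incomplete first dosing day remain unresolved on either reading. A shift smaller than the confidence interval is still bias, always in the favourable direction.

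Three stronger conclusions might be inferred, and the documents do not support them.

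- *That the bias is larger in Arm 2.* Section 3.0 reports discontinuation for adverse events in 26.5% of patients on the combination (Study D4190C00006) and 7.6% on monotherapy (ATLANTIC). The first figure pools tremelimumab doses of 3 and 10 mg/kg that the same section says were dropped for toxicity. The cohort to which this trial's fixed doses are described as equivalent had the fewest adverse events and discontinuations in that study; its any-AE rate was 77.8%, against 87.1% in ATLANTIC. These are cross-study figures for any time on treatment, not for cycle 1.
- *That a fatal first-cycle event vanishes from the Grade 3–4 rate because of this sentence.* A fatal event is Grade 5 and lies outside that rate under any safety set. It could leave the SAE rate, but only on the completed-cycle reading.
- *That all patients who stop in cycle 1 are certainly excluded.* That depends on a term the protocol does not define.

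**Conclusion.** The inconsistency is real and the point holds as a should-fix. Section 14.0 states a narrower safety set than Section 12.1 and than its own adverse-event tabulation. Applied as written, it can exclude patients because of the outcome being measured, so the toxicity, irAE and SAE rates can only be affected in the favourable direction by such exclusions.

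The extent depends on the undefined term: all cycle-1 toxicity stoppers on the completed-cycle reading, or only incomplete first dosing days on the other. The size cannot be obtained from the documents. Under the assumed range of 0 to 4 excluded events among 40 patients, the understatement runs from zero to 7.8 percentage points at a true 30% rate, and from zero to the full 10 points at a true 10% rate. The ORR, PFS and interim rules do not use this set, and the tie-break that uses safety would arise in at most about 2.5% of trials under equal true ORR.

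**What to change.** Replace the Section 14.0 sentence with: *For safety, all patients who received any amount of durvalumab or tremelimumab will be included, from the start of the first infusion.* State that this set applies, by arm, to every adverse event, irAE, SAE and Grade 3–4 toxicity rate and to the safety part of the winning-arm rule.

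This agrees with Section 12.1 and keeps all treated patients in the denominator, consistent with the 40 per arm behind the ±16%. The cost is one sentence. No new data are needed, and no dose or clinical rule changes. Reported toxicity may be slightly less favourable.
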